6.3 Measures to Minimize Bias: Randomization and Blinding

6.3.1 Randomization and Allocation Procedures

In each age group (18-49 years of age and \geq 50 years of age), eligible participants will be randomized in a 1:1 ratio through the Interactive Response Technology (IRT) to receive a single IM injection of either RIV4 or IIV4 at D01.

Site staff will connect to the IRT, enter the identification, security information, and confirm a minimal amount of data in response to IRT prompts. The IRT will then provide the dose number assignment and the site staff confirm it. The full detailed procedures for dose number allocation are described in the Operating Guidelines. If the participant is not eligible to participate in the study, then the information will only be recorded on the participant recruitment log.

Participant numbers that are assigned by the IRT consisting of a 12-digit string (a 3-digit country identifier, a 4-digit study center identifier, and a 5-digit participant identifier).

Participant numbers should not be reassigned for any reason. The randomization codes will be kept securely in the IRT system.

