9.4.1 General Considerations

All analyses will be descriptive and be provided by age groups and overall. No replacement will be done for safety and immunogenicity missing data and outliers. Analysis will be done using the collected values. Nevertheless, for unsolicited systemic AEs, missing relationship will be

considered as related to study vaccine(s) at the time of analysis. Details will be provided in the SAP.

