9.4.2 Immunogenicity

Descriptive analyses on HAI Ab response measured at D01 and D29 will be performed in each age, intervention group and pooled age group, including but will not be limited to:

- Geometric mean of HAI Ab titer (GMT) and 95% CI at D01 and D29
- Geometric mean fold-rise (GMFR) of HAI Ab titer and 95%CI. Fold-rise is computed as individual titer ratio of post-vaccination value divided by baseline value.
- Number and percentage of participants with seroconversion (seroconversion rate): titer < 10 (1/dilution [1/dil]) at D01 and post-injection titer ≥ 40 (1/dil) at D29, or titer ≥ 10 (1/dil) at D01 and a ≥ 4-fold increase in titer (1/dil) at D29
- Number and percentage of participants with titer $\ge 40 (1/dil)$ at D01 and D29
- Number and percentage of participants with detectable titer ≥ 10 (1/dil) at D01 and D29

The 95% CIs for the GMTs and GMT ratios (GMTRs) will be calculated using a normal approximation of log-transformed titers. The 95% CIs for the proportions will be based on the Clopper-Pearson method. The ratios of GMTs (RIV4/IIV4) in each age group will be obtained between groups with the 95% CIs calculated using a normal approximation of log-transformed titers. The differences in the seroconversion rates between groups in each age group will be computed along with the 2-sided 95% CIs by the Wilson-Score method without continuity correction. Additional parameters may be displayed as appropriate.

In addition, as a complementary analysis to support bridging discussion, Bayesian method will be used to evaluate the probability of non-inferiority in GMTs. The posterior probability of the true ratio of GMTs (RIV4/IIV4) to be higher than the commonly accepted non-inferiority margin (0.667) will be calculated using the Bayesian approach to support bridging with previous non-inferiority trials. Further details about the statistical methodology will be provided in the SAP.

Reverse cumulative distribution curves in each age group against each strain will be performed for baseline (D01) and post-vaccination immunogenicity (D29).

The Full Analysis Set (FAS) and Per-Protocol Analysis Set (PPAS) will be used for the main immunogenicity analyses. Details of both analyses' sets are described in Section 9.3.

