4.2.4.4	Duration of a Participant in the Active Phase	
4.2.4.5	Duration of the Active Phase	19
5	Changes in the Conduct of the Trial or Planned Analyses	20
6	Supporting Documentation	21
6.1	Appendix 1 List of Abbreviations	21
6.2	Appendix 2 Bayesian approach	23
7	References	27

List of Tables

Table 2.1: Objectives and endpoints	6
Table 3.1: Descriptive statistics produced	9

List of Figures

Figure 1.1: Graphical study	y design	5
-----------------------------	----------	---

1 Overall Design

[figure not shown]
This study is a Phase III, parallel, randomized, modified double-blind, active-controlled, multicenter clinical study planned to be conducted in 300 participants 18 years of age and older in South Korea to describe the immunogenicity and safety of the RIV4 versus a locally licensed IIV4 (Fluarix® quadrivalent) that will serve as a control arm.

In each age group (18-49 years of age and \geq 50 years of age), eligible participants will be randomized in a 1:1 ratio through the Interactive Response Technology (IRT) to receive a single intramuscular (IM) injection of either RIV4 or IIV4 at D01.

Participants will attend 2 visits and will provide a pre-vaccination blood sample (BL0001) at D01 and a post-vaccination blood sample (BL0002) at D29. The duration of each participant's participation will be approximately 6 months (180 days).

The design of the study is summarized in Table 4.1 of the protocol.

Figure 1.1: Graphical study design

Abbreviations: BL, Blood sampling; V, Visit; PC, Phone call

Detailed study design is provided in Sections 4.1 and 1.1 of the protocol.

2 **Objectives and Endpoints**

The study objectives and the corresponding endpoints are described in Table 2.1.

Table 2.1: Objectives and endpoints	Table 2.1:	Objectives	and	endpoints
-------------------------------------	-------------------	-------------------	-----	-----------

Primary* Objectives	Primary Endpoints	
Immunogenicity		
• To describe the immune response induced by RIV4 and IIV4 in 18-49 and ≥ 50 years of age participants by HAI measurement method.	 HAI antibody (Ab) titers obtained on Day (D) 01 and D29 Individual HAI titers ratio D29/D01 Seroconversion: titer < 10 (1/dilution [1/dil]) at D01 and post-injection titer ≥ 40 (1/dil) at D29, or titer ≥ 10 (1/dil) at D01 and a ≥ 4-fold increase in titer (1/dil) at D29 Titer ≥ 40 (1/dil) at D01 and D29 Detectable titer ≥ 10 (1/dil) on D01 and D29 	
Safety †		

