3.4 Statistical Analysis

3.4.1 General Considerations

The statistical analysis will be performed under the responsibility of the Sponsor's Biostatistics platform using SAS® Version 9.4 or later.

No hypotheses testing was planned in this study. All statistical analysis results will be provided by age group and by vaccine group. No replacement will be done for safety and immunogenicity missing data and outliers. Analysis will be done using the collected data. Nevertheless, for unsolicited systemic AEs, missing relationship will be considered as related to study vaccine at the time of analysis.

For descriptive purposes, the following statistics will be presented:

Disposition and	Categorical data	Number of participants
follow-up description	Categorical data	Percentage of participants
	Continuous data	Mean, standard deviation (SD), minimum and maximum.
Baseline	Categorical data	Number of participants.
characteristics		Percentage of participants.
	Continuous data	Mean, standard deviation (SD), quartiles, minimum and maximum.
Clinical safety results	Categorical data	Solicited: Number and percentage (95% CIs) of participants.
		Unsolicited: Number and percentage (95% CIs) of participants and number of events.
Immunogenicity results	Categorical data (seroconversion, cutoff)	Number and percentage (95% CIs) of participants.
	Continuous data	Log10: Mean and standard deviation.
	(titer / data)	Anti-Log10 (work on Log10 distribution, and anti- Log10 applied): Geometric mean, 95% CI of the geometric mean, quartiles, minimum, and maximum.
		Graphical representation by Reverse Cumulative Distribution Curve (RCDC).

 Table 3.1: Descriptive statistics produced

The CI for the single proportion will be calculated using the exact binomial method (Clopper-Pearson method, quoted by Newcombe (1), i.e., using the inverse of the beta integral with SAS®).

For immunogenicity results, assuming that Log10 transformation of the titers / data follows a normal distribution, at first, the mean and the 95% CI will be calculated on Log10 (titers / data) using the usual calculation for normal distribution (using Student's t distribution with n-1 degree of freedom), then antilog transformations will be applied to the results of calculations, in order to provide geometric means (GMs) and their 95% CI.

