3.4.2.1 Immunogenicity

The analysis of Hemagglutinin inhibition (HAI) Ab response measured at D01 and D29 will be performed by age subgroup, intervention group and pooled age group, including but will not be limited to:

- Geometric mean of HAI Ab titer (GMT) and 95% CI at D01 and D29
- Geometric mean fold-rise (GMFR) of HAI Ab titer and its 95%CI. Fold-rise is computed as individual titer ratio of post-vaccination value divided by baseline value.
- Number and percentage of participants with seroconversion (seroconversion rate): titer < 10 (1/dilution [1/dil]) at D01 and post-injection titer ≥ 40 (1/dil) at D29, or titer ≥ 10 (1/dil) at D01 and a ≥ 4-fold increase in titer (1/dil) at D29
- Number and percentage of participants with titer ≥ 40 (1/dil) at D01 and D29
- Number and percentage of participants with detectable titer ≥ 10 (1/dil) at D01 and D29

The 95% CIs for the GMTs and GMFR will be calculated using a normal approximation of log_{10} -transformed titers. The 95% CIs for the proportions will be based on the Clopper-Pearson method (1).

The ratios of GMTs (RIV4/IIV4) in each age group and pooled age group will be obtained between groups with the 95% CIs calculated using a normal approximation of log₁₀-transformed titers. The differences in the seroconversion rates between groups in each age group and pooled age group will be computed along with the 2-sided 95% CIs by the Wilson-Score method without continuity correction (2).

Reverse cumulative distribution curves in each age group and pooled age group against each strain will be performed for baseline (D01) and post-vaccination immunogenicity (D29).

The primary immunogenicity analyses will be performed on the Per-Protocol Analysis Set (PPAS) and on the Full Analysis Set (FAS). Details of both analyses sets are described in Section 3.3.

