6.2 Appendix 2 Bayesian approach

Calculation of the posterior probability of the GMT ratio being > 0.667

Based on Bayesian approach (3), we are going to calculate the posterior probability of the true GMT ratio for each strain between RIV4 and IIV4 to be higher than the commonly accepted non-inferiority margin (0.667), which is equivalent to true mean difference on the log_{10} scale > -0.176.

We assume that HAI log₁₀titer x_i for each strain for any group IIV4 or RIV4 follows normal distributions with known variance σ^2 . Considering the following sampling model for data from the two groups:

$$\begin{aligned} X_{i,1} = \mu + \delta + \epsilon_{i,1} \\ X_{i,2} = \mu - \delta + \epsilon_{i,2} \\ \{\epsilon_{i,j}\} \sim i. i. d. normal (0, \sigma^2) \end{aligned}$$

Using this parameterization where $\theta_1 = \mu + \delta$ and $\theta_2 = \mu - \delta$, representing group mean on the \log_{10} scale for each group. We see that δ represents half the population difference in means, as $(\theta_1 - \theta_2)/2 = \delta$, and μ represents the pooled average, as $(\theta_1 + \theta_2)/2 = \mu$. Assuming standard deviation of HAI \log_{10} titer is known and equal to the sample standard deviation for each strain. Sine σ is known, no prior is needed for it. Convenient conjugate prior distributions for the unknown parameters μ , δ are

$$p(\mu, \delta) = p(\mu) \times p(\delta)$$
$$\mu \sim normal(\mu_0, \gamma_0^2)$$
$$\delta \sim normal(\delta_0, \tau_0^2)$$

Then the full conditional distribution of μ and δ are as follows:

$$\{\mu | x_{i,1}, x_{i,2}, \delta, \sigma^2\} \sim normal(\mu_n, \gamma_n^2), \text{ where}$$
$$\mu_n = \gamma_n^2 \times [\mu_0 / \gamma_0^2 + \sum_{i=1}^{n_1} (x_{i,1} - \delta) / \sigma^2 + \sum_{i=1}^{n_2} (x_{i,2} + \delta) / \sigma^2]$$
$$\gamma_n^2 = [1 / \gamma_0^2 + (n_1 + n_2) / \sigma^2]^{-1}$$

$$\{\delta | x_{i,1}, x_{i,2}, \mu, \sigma^2\} \sim normal(\delta_n, \tau_n^2), \text{ where}$$

$$\delta_n = \tau_n^2 \times [\delta_0 / \tau_0^2 + \sum_{i=1}^{n_1} (x_{i,1} - \mu) / \sigma^2 - \sum_{i=1}^{n_2} (x_{i,2} - \mu) / \sigma^2]$$

$$\tau_n^2 = [1/\tau_0^2 + (n_1 + n_2) / \sigma^2]^{-1}$$

For the prior distribution of μ and δ , with reference to US studies (PSC12 and PSC16) we give prior settings as Appendix Table 1 shown. The priors on γ_0^2 and τ_0^2 tend to make these prior

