Appendix Table 1: prior settings for unknown parameters

Therefore, based on the above prior distribution, we can then calculate the posterior probability Pr ($2\delta > -0.176$ |data). The Markov chain Monte Carlo (MCMC) procedure is utilized to obtain samples from the posterior distribution. SAS example code is provided below.

The statistical criterion for demonstrating success (posterior probability threshold) is not proposed due to the not powered sample size and the nature of the descriptive study. But the corresponding threshold might be proposed in the bridge report for descriptive evaluation purpose.

Appendix Figure 1: Prior and posterior distributions for δ given a hypothetical observed data with $\delta = 0, \mu = 2.5, \sigma = 0.65$

```
SAS example code for the posterior probability calculation:
data aa;
 set add.adis;
 if paramn=1 and avisitn=2; ***paramn: parameter index in ADaM adis. Sample code only focus
on one parameter;
                 ***avisitn=2 is used to filter the post-vaccination titers.
 avallog=log10(aval);
 keep usubjid param paramn trt01pn trt01p aval avallog;
run;
/*==
     /*get the poopled mean and SD from data */
proc summary data=aa;
 var avallog;
 output out= stats(drop= type freq ) mean=mu pool n=n std=SD;
run;
/*got the group mean difference between RIV4 and IIV4*/
ods listing close;
ods output statistics = stats diff;
proc ttest data=aa alpha=0.05 ci=equal;
 class trt01pn ;
 var avallog;
run;
ods listing;
/*set initial value to mu pool, del; set SD as a fixed value obtained from data*/
proc sql noprint;
 select mean/2 into: del from stats diff (where=(method="Pooled"));
 select mu pool into: mu pool from stats ;
 select sd into: sd from stats ;
quit;
%put &del. &mu pool. &sd.;
/*======Start MCMC procedures:=====*/
/*generate posterior samples for mu and del*/
proc mcmc data=aa outpost=postout seed=123 nmc=10000 thin=2 monitor=( parms ) statistics;
                                      *** Postsumint= summary statistics;
 ods select PostSumInt;
 parm mu pool &mu pool. del &del.;
/* specify parameters to estimate and assign initial values to them*/
 prior mu_pool ~ normal(mean=2, var=1); /*specify prior distributions for the parameter mu that
represents the pooled average */
 prior del ~ normal(mean=-0.088, var=100);
```

Confidential/Proprietary Information Page 25 of 27 /*enable different avallog to have different mean and variance, depending on their group indicator*/

```
if trt01pn = 1 then do;

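### The pooled-age GMT ratio and seroconversion difference ignore the age stratum used in randomisation: the intervals are valid, but wider than needed if response differs by age

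*SAP*

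**What the plan says.** Protocol 6.3.1 makes age group a randomisation stratum: within each of the two age groups, "eligible participants will be randomized in a 1:1 ratio through the Interactive Response Technology (IRT) to receive a single IM injection". SAP 1 repeats this.

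Protocol 9.4.1 sets the reporting level: "All analyses will be descriptive and be provided by age groups and overall". Protocol 9.4.2 adds that the HAI analyses "will be performed in each age, intervention group and pooled age group, including but will not be limited to" the listed summaries. A pooled-age contrast is therefore within the protocol's scope.

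SAP 3.4.2.1 gives the method. GMT ratios for each age group and for pooled ages get 95% intervals from a normal approximation on log10 titers. For seroconversion, "The differences in the seroconversion rates between groups in each age group and pooled age group will be computed along with the 2-sided 95" per cent intervals, by the Wilson-score method without continuity correction. No age term, stratum weight or stratified variant is named, so the pooled contrasts are read here as unstratified.

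SAP Appendix 2 models log10 titer as an arm mean plus an error with variance σ². It then states that the standard deviation "is known and equal to the sample standard deviation for each strain". The example code obtains that value from PROC SUMMARY on both arms together, with no CLASS or BY statement ("output out= stats(drop= type freq ) mean=mu pool n=n std=SD"), and uses its square as the model variance.

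**The concern.** When age group is fixed by design and also predicts response, a two-sample interval on pooled ages treats the spread between age groups as noise. Balancing the arms on age has already removed that spread from the sampling error of the contrast, so the interval is longer than the design requires. The study tests no hypothesis and justifies its size by precision alone (Protocol 9.1 and 9.2), so interval width is what it delivers.

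There is a smaller second effect. If exclusions leave the arms with different age mixes, the unadjusted pooled ratio takes in part of the age difference.

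Appendix 2 has a related feature. A total SD contains the difference between arms and, if ages are pooled, the difference between age groups. The model's σ contains neither the arm difference nor, with an age term, the age difference.

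**Working it through.** **Inputs.** From SAP 3.2: 75 per cell, 5% drop-out, 71 evaluable per cell (142 per arm pooled), SD 0.65 on log10 titer. From SAP 3.4.2.3 and Appendix 2: margin 0.667 (log10 difference -0.176) and prior N(-0.088, 100) for δ. The size of any age difference is an assumption throughout.

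**1. The plan's own figures.** 75 × 0.95 = 71.25, so 71.
- Single proportion, Clopper-Pearson at 50%: width 24.2%.
- Difference, Newcombe Wilson-score at 50%: width 32.0%.
- Means, Student's t: 0.154 (single) and 0.216 (difference).

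All four agree with SAP 3.2. The SAP states no precision for the pooled-age contrast.

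**2. Pooled GMT ratio.** With A the log10 age difference and equal strata, the unstratified SD is √(0.65² + A²/4). With an age term it is 0.65. Half-width = 1.96 × SD × √(2/142).

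| Age difference | SD | Half-width | Extra width | CI at observed ratio 1.0 |
|---|---|---|---|---|
| none | 0.650 | 0.1512 | 0% | 0.706-1.416 |
| 1.5-fold | 0.656 | 0.1526 | 0.9% | 0.704-1.421 |
| 2-fold | 0.667 | 0.1552 | 2.6% | 0.700-1.430 |
| 3.2-fold | 0.697 | 0.1622 | 7.3% | 0.688-1.453 |

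The first row is also the stratified interval in every scenario. In 40,000 simulated trials per row, unstratified coverage was 94.9%, 95.3%, 95.6% and 96.5%; with an age term it was 94.9% to 95.1%.

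**3. Unequal age mix.** Suppose one arm ends with 75 younger and 67 older participants and the other with 71 and 71. The unadjusted ratio is multiplied by 10^[(75/142 - 71/142) × A] = 1.011, 1.020 and 1.033 for 1.5-, 2- and 3.2-fold.

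**4. Pooled seroconversion difference.** Mean widths in percentage points from 40,000 simulated trials per scenario, 71 per cell, no true vaccine difference, equal stratum weights:

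| Younger/older rate | Planned | Stratified, critical value rescaled | 95% stratum limits simply averaged |
|---|---|---|---|
| 60/60% | 22.4 | 22.4 | 31.3 |
| 70/60% | 21.9 | 21.7 | 30.3 |
| 80/60% | 21.1 | 20.5 | 28.6 |
| 70/40% | 22.8 | 21.7 | 30.3 |

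Combining the stratum distances by square-and-add within each arm gives 20.4 at 80/60% and 21.5 at 70/40%. Coverage is about 95% to 96% as planned, about 95% for the scaled stratified forms, and about 99.4% for simple averaging. Averaging is too wide because two half-widths, each based on 71 people, are averaged without allowing for the two strata being independent. With equal weights and variances the right multiplier is 1.96 × √(2 × 0.25) = 1.386, not 1.96.

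**5. Appendix 2, one age group at a time.** With D the observed log10 ratio and N = 142, total SD = √{[(N-2) × 0.65² + N × D²/4]/(N-1)}. At an observed ratio of 0.9 this is 0.648, and the posterior probability is 0.8844 against 0.8837 with 0.65. The change is below 0.001 at ratios from 0.7 to 1.5. At 0.5 it is 0.131 against 0.126.

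**6. Appendix 2, ages pooled.** With N = 284, total SD = √{[(N-4) × 0.65² + N × A²/4 + N × D²/4]/(N-1)}. At 3.2-fold, replacing 0.65 by the total SD moves the posterior from 0.954 to 0.943 at ratio 0.9, from 0.847 to 0.831 at 0.8, and from 0.276 to 0.291 at 0.6. So the direction is not fixed. The largest change at any ratio from 0.4 to 1.6 is 0.006, 0.010 and 0.020 for 1.5-, 2- and 3.2-fold.

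**The case against.** The strongest reply is that nothing here is an error. The study is descriptive, the immunogenicity objective is stated by age group, and those contrasts are specified separately. A simple pooled ratio also has the merit of matching the pooled GMTs tabulated beside it. At a 2-fold age difference the interval changes from 0.706-1.416 to 0.700-1.430, which would not alter a descriptive reading. All of that stands and sets the weight of the point. It does not remove the case for using a design factor already in the data at almost no cost.

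Three stronger readings are tempting and not supported.
- A reader might infer that the pooled intervals are invalid or biased. They are not: coverage is at or slightly above 95%, and with balanced cells and a common ratio the point estimate does not change.
- A reader might infer that the pooled contrast departs from the protocol, because the between-group sentences in Protocol 9.4.2 mention only each age group. Protocol 9.4.1 and the opening of 9.4.2 cover overall and pooled-age results.
- A reader might infer that Appendix 2 leaves sigma undefined. Its prose alone is loose, but the example code fixes it as the total SD of both arms. What remains is a mismatch with the error SD in the model.

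The pooled-posterior effect is also conditional. SAP 3.4.1 ("All statistical analysis results will be provided by age group and by vaccine group") and Protocol 9.4.1 imply by-age posteriors. Neither SAP 3.4.2.3 nor Appendix 2 says whether a pooled one will be given as well.

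**Conclusion.** The point holds as a modest gain in precision, worth considering rather than required. The pooled-age intervals are valid but ignore the randomisation stratum. The cost is nil without an age effect, about 1% to 3% of the log10 GMT-ratio width at 1.5- to 2-fold, and about 7% at 3.2-fold. For seroconversion it is 0 to about 1.3 points. An age mix of 75/67 against 71/71 would shift the unadjusted ratio by 1.1% to 3.3%. These sizes rest on SD 0.65, 71 per cell and age differences that the documents do not give. The age-specific results are unaffected.

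The sigma mismatch is minor: negligible by age at ratios 0.7 to 1.5, and at most 0.020 on a pooled posterior under the largest age difference assumed. No posterior threshold is set. Appendix 2 allows that one might be proposed in the bridge report, so the definition is better settled before then.

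**What to change.** **SAP 3.4.2.1, pooled age only.**
- GMT ratio: estimate it from a linear model on log10 titer with vaccine group and age group.
- Seroconversion difference: use a stratified Newcombe interval and write out its form. Either rescale the critical value within each arm, z × √(Σw²v)/Σ(w√v) with v the variance of the stratum rate, before weighting the stratum Wilson limits; or combine the weighted stratum distances by square-and-add within each arm. Then combine the two arms by square-and-add. Do not average the 95% stratum limits: that is about 33% to 40% wider than the planned interval (30.3/22.8 to 31.3/22.4).
- Leave the age-specific contrasts as planned.

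**Appendix 2.** Define sigma as the pooled within-arm SD, which the existing PROC TTEST step can supply. State whether a pooled-age posterior will be reported. If so, add an age term and use the within-arm, within-age SD, because the PROC TTEST value alone keeps the age component. At ratio 0.9 and a 2-fold age difference the total, within-arm, and within-arm-within-age SDs are 0.664, 0.665 and 0.650, giving posteriors of 0.951, 0.951 and 0.954.

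**Cost.** SAP wording and a few lines of SAS, with no new data. The slight over-coverage is given up. The adjusted ratio assumes a common ratio across ages and can differ from the simple ratio of the tabulated pooled GMTs. For example, take age-specific ratios of 1.2 (younger) and 1.0 (older), a 2-fold age difference, and cells 75/67 against 71/71. The adjusted weights are 75 × 71/146 = 36.5 and 67 × 71/138 = 34.5, giving 1.2^(36.5/71.0) = 1.098. The simple ratio is 10^[(75/142) × log10 2.4 - (71/142) × log10 2] = 1.123. With balanced cells both are 1.095. A sentence in the SAP should say which pooled ratio is reported; the age-specific results alongside let the reader judge the common-ratio assumption.
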